4.6.5.5.3. Definitions of Participant ADA Status

Treatment-emergent (TE) ADA-evaluable participants: a participant with a nonmissing baseline ADA result and at least 1 nonmissing postbaseline ADA result.

Treatment-emergent ADA unevaluable participant: any participant who does not meet the evaluable criteria.

Baseline ADA Present (preexisting antibody): ADA detected in a sample collected up to the first dose date and time.

Baseline ADA Not Present: ADA is not detected, and the corresponding tirzepatide PK concentration is missing or below the drug tolerance limit in a sample collected up to the first dose date and time.

TE ADA positive (TE ADA+) participant: A participant who is evaluable for TE ADA is TE ADA+ if either of the following holds:

- The participant has baseline status of ADA Not Present and at least 1 postbaseline status of ADA Present with titer $\geq 2 \times$ MRD of the ADA assay.
- The participant has baseline and postbaseline status of ADA Present, with the postbaseline titer being 2 dilutions (4-fold) greater than the baseline titer. That is, the

participant has baseline (B) status of ADA Present, with titer 1:B, and at least 1 postbaseline (P) status of ADA Present, with titer 1:P, with P/B \geq 4.

As shown in [Figure GPHL.4.1](#), a titer is expected when ADA assay result is detected. On occasion, the corresponding assay cannot be performed, in which case a titer value will be imputed for the purpose of TE ADA determination. A baseline sample with detected ADA and no titer is imputed to be the MRD (1:10) and a postbaseline sample with ADA detected and no titer is imputed to be one dilution above the MRD (1:20).

TE ADA-Inconclusive participant: a TE ADA-evaluable participant is TE ADA Inconclusive if \geq 20% of the participant's postbaseline samples are ADA Inconclusive and all remaining postbaseline samples are ADA Not Present.

TE ADA-negative (TE ADA-) participant: a TE ADA-evaluable participant is TE ADA- when the participant is not TE ADA+ and not TE ADA Inconclusive.

For each NAb assay, the following is defined:

NAb-positive (NAb+) participant: a participant who is TE ADA+ and has a Nab+ sample in the postbaseline period.

NAb-Inconclusive participant: a participant who is TE ADA+, is not NAb+, and all samples that have TE ADA+ titer have a NAb-Inconclusive sample result.

NAb-negative (NAb-) participant: a participant is neither NAb+ or NAb inconclusive.

Unless specified otherwise, the above-mentioned definitions of NAb are applicable to all NAb analyses, including cross-reactive NAb analyses, and cross-reactive antibodies.

4.6.5.5.4. Analyses to be Performed

The count and proportion of participants who are TE ADA+ will be tabulated by treatment group, where proportions are relative to the number of TE ADA-evaluable participants, as defined above. The tabulation will include the count and proportion of participants with ADA Present at baseline and the count and proportion of TE ADA+ participants exhibiting each type of cross-reactive antibodies and NAb. This analysis will be performed for

- the planned treatment period, and
- the entire postbaseline period including safety follow-up.

The *in silico* classification for cross-reactive NAb will be summarized.

A summary will be provided of the count and percentage of tirzepatide-treated participants experiencing specific TEAE (see [Table GPHL.4.10](#)) by TE ADA status (TE ADA+, TE ADA-, TE ADA Inconclusive) during the planned treatment period.

Table GPHL.4.10. Adverse Events for Analysis with Immunogenicity Results

TEAE category	Criteria
Hypersensitivity reactions	Anaphylaxis SMQ (narrow or algorithm)
	Hypersensitivity SMQ (narrow)
	Angioedema SMQ (narrow)
	Severe Cutaneous Adverse Reaction SMQ (narrow)
	Vasculitis SMQ (narrow)
Injection site reactions	Injection site reaction HLT
	Infusion site reaction HLT
	Administration site reaction HLT

Abbreviations: HLT = High Level Term; MedDRA = Medical Dictionary for Regulatory Activity; SMQ = Standardised MedDRA Query; TEAE = treatment-emergent adverse event.

A listing will be provided for all participants who had ADA Present at any time (including baseline) or had any specific TEAE (see [Table GPHL.4.10](#)). This listing includes a time course of ADA (clinical interpretation result plus flags for samples meeting TE ADA+ criteria and for samples with cross-reactive antibodies and NAb present) along with the TEAE.

Cases of TE ADA that are associated with TEAEs of either severe/serious hypersensitivity or injection site reactions will be classified as AESIs.

Additional immunogenicity analyses as determined later may be presented. The relationship between antibody titers, the PK parameters, and PD response to tirzepatide may also be assessed.

4.6.5.6. Hypersensitivity Reactions

Two main analyses are performed in support of assessment of potential immediate hypersensitivity, including anaphylaxis, as well as potential nonimmediate hypersensitivity.

Time Period A, of potential immediate hypersensitivity includes all TEAEs occurring from start of study drug administration up to 24 hours after end of study drug administration. For events without the hypersensitivity eCRF, only date (no time) information are collected; if such events occurred on the same date as the study drug injection date, they will be included in Time Period A.

Time Period B, of potential nonimmediate hypersensitivity, includes all TEAEs occurring more than 24 hours after the end of study drug administration, but prior to subsequent drug administration.

The counts and percentages of participants who experienced a hypersensitivity TEAE will be summarized by PT with decreasing frequency by treatment.

Analyses for both time periods are based on the following:

- Narrow and algorithm terms in Anaphylactic reaction SMQ (20000021) (Note that Anaphylactic reaction SMQ algorithm will only be summarized for Time Period A)
- Narrow terms in Angioedema SMQ (20000024)
- Narrow terms in Severe cutaneous adverse reactions SMQ (20000020)
- Narrow terms in Hypersensitivity SMQ (20000214), and

- Narrow terms in Vasculitis SMQ (20000174)

For the Anaphylactic reaction SMQ, each term is classified by scope (Narrow, Broad) and by category (A, B, C, D). All Narrow terms are category A, and all Broad terms are category B, C, or D. In addition to the usual Narrow and Broad searches, the SMQ defines an algorithm to further refine the cases of interest. For the analysis of time period A, the Anaphylactic reaction SMQ algorithm will be included. The algorithm is based upon events that occur within Time Period A.

The counts and percentages of participants who experienced a TEAE for the following will be analyzed for each of the 2 time periods:

- Any narrow term from any one of the 5 SMQs indicated above (ie, combined search across narrow of all 5 SMQs)
- Any narrow term within each SMQ, separately (ie, narrow SMQ search).

Within query, individual PTs that satisfied the queries will be summarized. Also, a single event may satisfy multiple SMQ, in which case the event contributes to every applicable SMQ.

4.6.5.6.1. Severe/Serious Hypersensitivity Reactions

The severe/serious cases of treatment-emergent hypersensitivity will be considered as AESIs. A summary with severe/serious hypersensitivity reactions may be provided, if deemed necessary.

4.6.5.7. Injection Site Reaction

Injection site reactions, incidence and rates, and related information reported via the “Injection Site Reactions” eCRF will be summarized by treatment. Information to be summarized includes the location of the reaction, timing of the reaction relative to study drug administration, and characteristics of the injection site reaction: erythema, induration, pain, pruritis, and edema.

Patient-based analysis and event-based analysis may be provided if necessary. The patient-based analysis summarizes all ISR questionnaire forms for an individual patient with a single statistic, typically an extreme value. This analysis allows each patient to contribute only once for each parameter, at the expense of a focus on the most extreme events. By contrast, the event-based analysis summarizes all ISR questionnaire forms received, without regard to individual patients. This provides characteristics of ISR events as a proportion of all events for which questionnaire responses were provided, at the expense of some potential bias due to differential contribution of individual patients to the analysis.

The counts and percentages of participants with treatment-emergent ISRs will be summarized by treatment using the MedDRA PTs. Detailed searching criteria can be found in Appendix 6.6 (Section 6.6).

The PT will be summarized in decreasing order of incidence for tirzepatide-treated participants.

4.6.5.7.1. Severe/Serious Injection Site Reactions

The severe/serious treatment-emergent injection site reactions based on TEAE search criteria specified in Appendix 6.6 (Section 6.6) will be considered as AESIs.

The counts and percentage of participants with severe/serious treatment-emergent ISRs will be summarized by treatment. A listing of participants with treatment-emergent severe/serious ISRs may be provided, if deemed necessary.

4.6.5.8. Major Adverse Cardiovascular Events

The following positively adjudicated MACE will be considered as AESIs:

- death due to cardiovascular AEs
- myocardial infarction
- hospitalization for unstable angina
- hospitalization for heart failure
- coronary interventions (such as coronary artery bypass graft or percutaneous coronary intervention), and
- cerebrovascular events, including cerebrovascular accident (stroke) and transient ischemic attack.

The counts and percentages of participants with positively adjudicated MACE may be summarized by treatment.

In addition, MACE reported by investigator may also be summarized although a MACE reported by investigator and not positively adjudicated is not considered as AESI.

A listing of participants reporting MACE events, either reported by investigator or identified by the CEC, will be provided.

4.6.5.9. Major Depressive Disorder/Suicidal Ideation or Behavior

The severe/serious treatment-emergent major depressive disorder/suicidal ideation or behavior will be captured as AESI. Adverse events will be searched using MedDRA PT terms. Detailed searching criteria can be found in Appendix 6.6 (Section 6.6).

The counts and percentages of participants with TEAEs will be summarized by treatment group using MedDRA PT nested within SMQ. Events will be ordered by decreasing frequency nested within SMQ. A listing of participants with major depressive disorder/suicidal ideation or behavior may be provided if deemed necessary.

In addition to spontaneously reported AEs assessed by the investigator, suicidal ideation and behavior, and depression will be assessed through the use of the C-SSRS and the (PHQ-9), respectively.

4.6.5.9.1. Patient Health Questionnaire

Total scores for the PHQ-9 range from 0 to 27 with total scores categorized as

- none (not depressed): 0 through 4
- mild: 5 through 9
- moderate: 10 through 14
- moderately severe: 15 through 19, and
- severe: 20 through 27.

Shift tables will be provided showing the counts and percentages of participants within each baseline category (maximum value) versus each postbaseline category (maximum value) by treatment.

Additionally, the following 3 outcomes of interest will be compared between treatments (based on the maximum value during baseline and postbaseline):

- any increase in depression category (that is, worsening of depression): includes participants in the none, mild, moderate, or moderately severe category during baseline and with at least 1 postbaseline measurement
- increase from No or Mild Depression to Moderate, Moderately Severe or Severe Depression: includes participants in the none or mild depression category during baseline and with at least 1 postbaseline measurement; and
- increase from Mild or Moderate Depression to Moderately Severe or Severe Depression: includes participants in the mild or moderate depression category during baseline and with at least 1 postbaseline measurement

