	Diabetes education to be performed by personnel who are qualified to educate participants on symptoms and management of hyperglycemia and hypoglycemia, SMBG, self-injection, and diabetes management. Participants are required to measure fasting SMBG values weekly and record them in the study diary. It is recommended that participants measure their fasting glucose on the same day each week. All trainings should be repeated as needed to ensure participant compliance.																								
Dispense BG meter/supplies as needed		X	X	X	X	X	X	X	X			X			X			X			X			X	
Remind participants about 7-point SMBG		X						X												X					
	Participant is required to collect two 7-point SMBGs on nonconsecutive days within 2 weeks prior to the next visit. A 7-point SMBG consists of measurements before and 2 hours after each of 3 main meals within the same day and at bedtime.																								
Injection training with autoinjector demonstration device			X																						
Participant Diary (paper)																									
Dispense diary, instruct in use		X	X	X	X	X	X	X	X			X			X			X			X			X	
	All training should be repeated as needed to encourage participant compliance.																								
Diary review, including hypoglycemia			X	X	X	X	X	X	X	X	X	X	X	X	X	X	X	X	X	X	X			X	X
Review 7-point SMBG values collected in the diary			X						X														X		
Patient Reported Outcomes																									
PGIs	X		X																				X	X	
SF-36v2 acute form	X		X																				X	X	

Visit	1	2	3	4	5	6	7	8	9	10	11	12	13	14	15	16	17	18	19	20	21	99	ED	801
Week of Treatment	-3	-2	0	4	8	12	16	20	24	28	32	36	40	44	48	52	56	60	64	68	72	72		4 wks post end of TxP
Allowable Interval Tolerance (days)		±3	±7	±3	+7	±3	+7	±3	±3	±3	±3	+7	±3	±3	±3	±3	±3	±3	±3	±3	±7	±7		±3
Fasting Visit	X		X	X	X	X	X	X	X			X			X			X			X	X	X	X
Telephone Visit										X	X		X	X		X	X		X	X				
IWQOL-Lite-CT	X		X																			X		X
EQ-5D-5L			X																			X		X
Mental Health Questionnaires																								
Patient Health Questionnaire-9 (PHQ-9)	X		X			X			X			X			X			X			X	X	X	X
PHQ-9 is self-administered and should be completed after assessment of adverse events.																								
Columbia-Suicide Severity Rating Scale (C-SSRS) (Baseline/Screening Version)	X																							

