Note: Participants with a history of subclinical hypothyroidism but a TSH at screening within the range indicated above, may be included if, in the investigator's opinion, the participant is unlikely to require initiation of thyroid hormone replacement during the course of the study.

19. Have obesity induced by other endocrinologic disorders (for example Cushing syndrome) or diagnosed monogenetic or syndromic forms of obesity (for example, Melanocortin 4 Receptor deficiency or Prader Willi Syndrome)
20. Have a history of significant active or unstable Major Depressive Disorder (MDD) or other severe psychiatric disorder (for example, schizophrenia, bipolar disorder, or other serious mood or anxiety disorder) within the last 2 years

Note: Participants with MDD or generalized anxiety disorder whose disease state is considered stable for the past 2 years and expected to remain stable throughout the course of the study, in the opinion of the investigator, may be considered for inclusion if they are not on excluded medications.

21. Have any lifetime history of a suicide attempt
22. Have a PHQ-9 score of 15 or more on or before Visit 3
23. On the C-SSRS at Visits 1, 2, or 3, prior to randomization:

- a "yes" answer to Question 4 (Active Suicidal Ideation with Some Intent to Act, Without Specific Plan) on the "Suicidal Ideation" portion of the C-SSRS

or

- a "yes" answer to Question 5 (Active Suicidal Ideation with Specific Plan and Intent) on the "Suicidal Ideation" portion of the C-SSRS

or

- a "yes" answer to any of the suicide-related behaviors (actual attempt, interrupted attempt, aborted attempt, preparatory act or behavior) on the "Suicidal Behavior" portion of the C-SSRS

and

- the ideation or behavior occurred within the past month
24. Have uncontrolled hypertension (systolic blood pressure [SBP] ≥ 160 mmHg and/or diastolic blood pressure ≥ 100 mmHg)
 25. Have any of the following cardiovascular conditions within 3 months prior to randomization: acute myocardial infarction, cerebrovascular accident (stroke), unstable angina, or hospitalization due to congestive heart failure (CHF)
 26. Have NYHA Functional Classification class IV CHF
 27. Have acute or chronic hepatitis, signs and symptoms of any liver disease other than nonalcoholic fatty liver disease (NAFLD), or any of the following, as determined by the central laboratory during screening:
 - alanine aminotransferase (ALT) level $>3.0X$ the upper limit of normal (ULN) for the reference range,

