9.4.4.4.3. Depression, Suicidal Ideation and Behavior

In addition to the summary of TEAEs, suicidal ideation and behavior will be assessed by C-SSRS, and depression related symptoms will be assessed using PHQ-9.

The analysis details will be provided in the SAP.

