4.1. General Considerations

Statistical analysis of this study will be the responsibility of Lilly or its designee. Some analyses and summaries described in this analysis plan may not be conducted if not warranted by data (eg, few events to justify conducting an analysis). Additional analyses of the data may be conducted as deemed appropriate.

Unless otherwise noted, tests of treatment effects will be conducted at a 2-sided alpha level of 0.05, and the CI will be calculated at 95% 2-sided.

Unless specified otherwise, efficacy and safety will be assessed using the mITT population, and data will be analyzed based on the assigned treatment (ie, not the actual treatment received by the participant).

Summary descriptive statistics for continuous measures will include sample size, mean, SD, median, minimum, and maximum. The analysis model to make comparisons among treatment groups relative to continuous measurements assessed over time will be either ANCOVA or a MMRM.

Kaplan-Meier method will be used for estimation of cumulative event-free survival rates over time, and Cox proportional hazards regression analysis will be used to compare hazards rates among treatments.

Summary statistics for categorical measures (including categorized continuous measures) will include sample size, frequency, and percentages. Logistic regression will be used to examine the treatment difference in binary efficacy outcomes if there is a need to adjust for covariate. Otherwise, Fisher's exact test will be used to examine the treatment difference.

Summary statistics for discrete count measures will include sample size, mean, SD, median, minimum, and maximum.

Unless specified otherwise, baseline will be defined as the last available nonmissing measurement during Visit 1 to Visit 3. For the safety-related parameters, the definition of baseline and postbaseline are specified in [Table GPHL.4.1](#).

Table GPHL.4.1. Baseline and Postbaseline Definitions for Safety Groups

Analysis Set	Analysis Type	Baseline	Postbaseline
SS	(1.1) Treatment-Emergent Adverse Events	The baseline period is defined as the start of screening and ends prior to the first dose of study treatment (typically at Week 0).	Starts after the first dose of study treatment and ends at the end of the study period (including off-drug follow up visit).

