4.6. Safety Analyses

Unless specified otherwise, safety assessments will be based on the SS (Table GPHL.3.1). All events that occur between the first dose date of study drug and the end date of study participation will be included, regardless of the adherence to study drug.

The statistical assessment of homogeneity of the distribution of categorical safety responses between tirzepatide doses and placebo will be conducted using Fisher's exact test, unless specified otherwise.

For selected continuous safety parameters, the mean change from baseline versus placebo will be assessed via a MMRM using REML. Data from scheduled visits will be utilized for this analysis. Unless specified otherwise, the model will include country/pooled country, sex, type of AHM used at randomization, treatment group, visit and treatment-by-visit interaction as fixed effects, and baseline value of the safety parameter as a covariate. To model the covariance structure within participants, the unstructured covariance matrix will be used. If this model fails to converge, the covariance structures specified in Section 4.3.2.2 will be tested in order until convergence is met. If the data does not warrant the MMRM model, then ANCOVA model will be conducted.

For selected safety parameters, time-to-first-event analysis via the Cox-proportional hazards model may be conducted. Participants without the event will be censored at the end of study participation. For participants experiencing the event, the “time-to-first-event” will be the time (in weeks) from first dose to first occurrence of the event.

Where necessary, the rate of events will be analyzed using a generalized linear mixed-effects model assuming the number of events follow a negative binomial distribution and with treatment as a fixed effect. The logarithm of days during the active treatment period will be adjusted as an offset to account for possible unequal treatment duration of follow-up among participants.

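### SAP 4.6.5.9.1 compares PHQ-9 between arms only as category increases of the maximum score and commits to no analysis of the 0–27 total, so it is less sensitive to a general worsening of depressive symptoms

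*SAP*

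**What the plan says.** Protocol 9.4.4.4.3 says only that "depression related symptoms will be assessed using PHQ-9" and leaves the method to the SAP.

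SAP 4.6.5.9.1 opens with "Total scores for the PHQ-9 range from 0 to 27 with total scores categorized as" and lists five severity bands (0–4, 5–9, 10–14, 15–19, 20–27). It plans shift tables of the maximum baseline band against the maximum postbaseline band. It then says: "Additionally, the following 3 outcomes of interest will be compared between treatments (based on the maximum value during baseline and postbaseline". The three outcomes are any rise in band, a rise from none or mild to moderate or worse, and a rise from mild or moderate to moderately severe or worse. The section names no model.

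For safety data in general, SAP 4.6 says "For selected continuous safety parameters, the mean change from baseline versus placebo will be assessed via a MMRM using REML". PHQ-9 is neither named nor excluded there.

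**The concern.** Reducing a participant's scores to the band of one maximum discards movement within a band and most of the repeated measurement. The maximum of six or more postbaseline scores is also set against the maximum of two baseline scores, so a share of participants in every arm move up a band by chance. That does not bias the comparison, but it adds noise to it.

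Protocol 8.2.6 describes this population as being at raised risk of depression, and severe or serious depression or suicidality is an adverse event of special interest. As written, the plan could miss a modest general rise in symptoms. It also commits to no estimate or interval for the score difference, which would be informative even if no test were significant.

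**Working it through.** **1. Data available.** The PHQ-9 row of the Schedule of Activities (Protocol 1.3) marks Visits 1 and 3, then Weeks 12, 24, 36, 48, 60 and 72, plus Visit 99, early discontinuation and Visit 801. That is two baseline and six scheduled treatment-period scores per completer.

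**2. Is a total-score analysis already committed?** Where the SAP wants a mean-change model for a safety topic, it says so in the topic section: vital signs (4.6.3.4), pancreatic enzymes (4.6.5.1.1), and eGFR and UACR (4.6.5.11). Section 4.6.5.9.1 does not. The analysis is permitted but not promised.

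**3. The plan's own power figure.** The only stated power is more than 90% for the weight endpoints. With 300 × (1 − 0.25) = 225 per arm, difference 11, SD 10 and alpha 0.025, the number needed per arm for 90% is 2 × (2.2414 + 1.2816)² × (10/11)² ≈ 21. Power at 225 is about 1.00, so the figure reproduces. It has no bearing on PHQ-9, for which no power is stated.

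**4. Simulation inputs.**
- From the documents: 300 per arm; 25% dropout; the exclusion "Have a PHQ-9 score of 15 or more on or before Visit 3"; the default that "The statistical assessment of homogeneity of the distribution of categorical safety responses between tirzepatide doses and placebo will be conducted using" Fisher's exact test; and "tests of treatment effects will be conducted at a 2-sided alpha level of 0.05".
- Assumed, because the documents give no PHQ-9 distribution: either a gamma/overdispersed Poisson score (mean/shape 3/0.8, 4/1.0 or 2.5/0.6) or a log-normal type score (mean 2.5 or 4.0, CV about 1, within-person correlation 0.5 or 0.7).
- Comparator: ANCOVA of the mean postbaseline score on arm and baseline, standing in for a mixed-model contrast averaged over visits.
- Designs, one dose against placebo: A, 300 per arm, 25% monotone dropout, six postbaseline scores, 300 trials per setting; B, 225 per arm, six postbaseline scores, gamma; C, 300 per arm, 25% monotone dropout, seven postbaseline scores, log-normal, 400 trials per setting.
- Monte Carlo standard error at 50% power with 300 trials: √(0.5 × 0.5 / 300) = 0.029, about 3 points.

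**5. General worsening.** Power ranges over the assumed distributions:

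| Harm and design | Any rise in band (best planned outcome) | Visit-averaged score |
|---|---|---|
| 15% rise, gamma (A) | 21–27% | 46–55% |
| 15% rise, log-normal (A) | 50–62% | 89–96% |
| 25% rise, gamma (A) | 45–62% | 81–90% |
| 25% rise, gamma (B) | 42–57% | 88–95% |
| 25% rise, log-normal (A) | 90–97% | 100% |
| +0.5 point in everyone (C) | 27–32% | 82–100% |
| +1.0 point in everyone (C) | 86–92% | 100% |

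Comparing within the same distribution, the gain at a 15% rise was 25 to 44 points. At a 25% rise it was 38 to 46 points under gamma (B), but only 100 − 97 = 3 to 100 − 90 = 10 points under log-normal, where the planned outcome has little room left to improve.

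**6. Week 72 alone.** For a 25% rise, against any rise in band, it gave 48–62% versus 38–58% (a repeat of B), 36–49% versus 45–62% (A, gamma) and 76–92% versus 91–97% (C). For a uniform +0.5 point it gave 40–85% versus 27–32% (C). It is not reliably better; the consistent gain comes from averaging over visits.

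**7. Harm confined to a subset** (+10 points at two visits), none/mild to moderate-or-worse against the averaged score:
- 10% of participants: 48–95% versus 34–64% (C); 50–66% versus 30–41% (gamma, 225 per arm).
- 5% of participants: 14–48% versus 12–25% (C).

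Here the planned outcome is the stronger test.

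**8. No drug effect.** Between 18% and 40% of simulated placebo participants rose a band by chance (A). Rejection rates were 2–6% for all the tests (C), so neither approach is invalid.

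**The case against.** The strongest reply is that nothing here is an error. The protocol hands the method to the SAP, the SAP specifies it, and no power is claimed for any safety outcome. The bands suit how the documents use the instrument: a score of 15 or more excludes at entry, and on study it prompts referral to a mental health professional and consideration of stopping study drug. A maximum catches a transient episode that averaging would smooth away. Depression is also followed through adverse events, and suicidality through the C-SSRS. The SAP 4.6 clause and the allowance in SAP 4.1 for additional analyses leave a mean-score model open. Nothing in the documents marks a shift of 0.6 to 1.0 point on a 27-point scale (the assumed 25% rise) as clinically meaningful.

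Most of this stands, and it is why the categorical outcomes should stay. It does not remove the gap. The two approaches detect different forms of harm, and the plan commits to only one. An optional clause is weaker than the explicit commitments made for other safety topics.

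A reader might go further and infer that the plan has far less power in general, or that the report will certainly contain no score estimate. The documents support neither. The first depends on an assumed distribution and form of harm, and reverses for a subset. The second overlooks the SAP 4.6 clause.

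**Conclusion.** The point holds as a gap in sensitivity and reporting, not as a mistake or contradiction. The planned comparisons have less power than a visit-averaged total score against a general worsening, and no score difference with an interval is committed.

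The size is conditional: roughly 25 to 45 points of power for a 15% proportional rise, and from a few points (log-normal) to about 45 (gamma) for a 25% rise. For sharp worsening in 5–10% of participants the ranking reverses. These figures rest on assumed PHQ-9 distributions and an ANCOVA stand-in for the mixed model, so they show direction and plausible range and do not forecast this trial. A low-cost addition is worth making.

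**What to change.** Add to SAP 4.6.5.9.1: change from baseline in PHQ-9 total score will be analysed with the Section 4.6 mixed model, with baseline PHQ-9 total score as covariate; the main contrast is the difference of each dose from placebo averaged over the postbaseline treatment-period visits (Weeks 12 to 72), reported with a 95% CI; Week 72 results are descriptive. Keep the shift tables and all three categorical outcomes.

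The cost is one SAP sentence and one more run of an existing model on data already collected. The downside is small: one more unadjusted safety comparison (SAP 2.1 makes no multiplicity adjustment for safety), on a skewed score whose mean difference should be read alongside the categories.

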8.3.2.13. Depression, Suicidal Ideation or Behavior Monitoring

Participants will be monitored for depression and suicidal ideation or behavior through AE collection and by using the C-SSRS and the PHQ-9. Participants will be referred to a MHP if in the opinion of the investigator it is necessary for the safety of the participant or if the participant had any of the following:

- a PHQ-9 score ≥ 15
- C-SSRS responses of:
 - A “yes” answer to Question 4 (Active Suicidal Ideation with Some Intent to Act, Without Specific Plan) on the “Suicidal Ideation” portion of the C-SSRS
 - or**
 - A “yes” answer to Question 5 (Active Suicidal Ideation with Specific Plan and Intent) on the “Suicidal Ideation” portion of the C-SSRS
 - or**
 - A “yes” answer to any of the suicide-related behaviors (actual attempt, interrupted attempt, aborted attempt, preparatory act, or behavior) on the “Suicidal Behavior” portion of the C-SSRS

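### The one PHQ-9 comparison between arms whose event is a score of 15 or more leaves out participants with a baseline of 0 to 4, so no named comparison covers everyone who reaches the protocol's referral score

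*SAP*

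**What the plan says.** SAP 4.6.5.9.1 divides the PHQ-9 total score into five categories. The bottom one is "none (not depressed): 0 through 4"; mild is 5 to 9 and moderate is 10 to 14; the top two are "moderately severe: 15 through 19, and" "severe: 20 through 27". A shift table of maximum baseline against maximum postbaseline category is planned by treatment. In addition, "the following 3 outcomes of interest will be compared between treatments (based on the maximum value during baseline and postbaseline":

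- Outcome 1 is any rise in category. Its population "includes participants in the none, mild, moderate, or moderately severe category during baseline and with at least 1 postbaseline measurement".
- Outcome 2 is a rise to moderate or worse (10 or more) among participants with no or mild depression at baseline.
- Outcome 3 is "increase from Mild or Moderate Depression to Moderately Severe or Severe Depression: includes participants in the mild or moderate depression category during baseline".

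The protocol uses a score of 15 in three places. Exclusion criterion 22 in Section 5.2 is "Have a PHQ-9 score of 15 or more on or before Visit 3". Section 8.3.2.13 begins "Participants will be referred to a MHP if in the opinion of the investigator it is necessary for the safety of the participant" and then lists a PHQ-9 of 15 or more among the specific triggers for referral. Section 7.1 lists the same score among possible reasons for permanently stopping study drug, with referral to help make that decision. Protocol 9.4.4.4.3 leaves the details of the PHQ-9 analysis to the SAP.

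**The concern.** A score of 15 is the level of depression on which this protocol acts, so a natural safety question is whether more participants on tirzepatide than on placebo reached it. Outcome 3 is the only compared outcome aimed at that score, and it does not include participants who had no depression at entry. A participant who goes from 2 to 22 is not an event in it and is not in its denominator.

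In a trial that admitted scores of 15 or more, a mild-or-moderate restriction would at least remove people already above the cut. Here criterion 22 has done that, so among eligible participants the restriction removes exactly one group: those in whom a score of 15 or more would be new onset rather than worsening. At stake is how directly the planned comparisons answer the question, in a topic (major depression and suicidality) that Protocol 9.4.4.3 lists as of special interest.

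**Working it through.** The plan states no figure to reproduce here, so the check has two parts: applying the three definitions to every possible move, and sizing the gap under stated assumptions.

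**1. Which moves each outcome counts.** Criterion 22 covers scores up to and including Visit 3, so an eligible participant has a maximum baseline of 0 to 14 (none, mild or moderate). The upward category moves open to such participants are:

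| Baseline to postbaseline | Reaches 15 or more | Outcome 1 | Outcome 2 | Outcome 3 |
|---|---|---|---|---|
| None to mild | no | yes | no | no |
| None to moderate | no | yes | yes | no |
| None to moderately severe | yes | yes | yes | **no** |
| None to severe | yes | yes | yes | **no** |
| Mild to moderate | no | yes | yes | no |
| Mild to moderately severe | yes | yes | yes | yes |
| Mild to severe | yes | yes | yes | yes |
| Moderate to moderately severe | yes | yes | no | yes |
| Moderate to severe | yes | yes | no | yes |

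Six moves reach 15 or more, and outcome 3 counts four of them. Outcome 1 counts all six but mixes them with three moves that stay below 15. Outcome 2 counts four of the six, mixes them with two that stay below 15, and leaves out participants who are moderate at baseline. None of the three outcomes is the set of all participants reaching 15 or more.

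**2. Size.** The documents give neither the baseline PHQ-9 distribution nor any risk of reaching 15. Assumptions:

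- N = 900 randomized (Protocol 9.2), all with a postbaseline score
- share s with baseline 0 to 4: 60% to 80%
- risk r0 of reaching 15 or more in that group: 0.5% to 1%
- risk r1 in the mild or moderate group: 3% to 5%

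Share of events missed by outcome 3 = s·r0 / [s·r0 + (1 − s)·r1].

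- Lowest (s = 60%, r0 = 0.5%, r1 = 5%): 540 × 0.005 = 2.7 events missed and 360 × 0.05 = 18.0 counted; 2.7 / 20.7 = 13%.
- Middle example (s = 70%, r0 = 1%, r1 = 3%): 630 × 0.01 = 6.3 missed and 270 × 0.03 = 8.1 counted; 6.3 / 14.4 = 44%.
- Highest (s = 80%, r0 = 1%, r1 = 3%): 720 × 0.01 = 7.2 missed and 180 × 0.03 = 5.4 counted; 7.2 / 12.6 = 57%.

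The denominator of outcome 3 is (1 − s) × 900 = 180 to 360 participants, or 60 to 120 per arm of 300.

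Total events of 15 or more on the same grid run from 720 × 0.005 + 180 × 0.03 = 3.6 + 5.4 = 9.0 up to 540 × 0.01 + 360 × 0.05 = 5.4 + 18.0 = 23.4. That is about 3 to 8 per arm if spread evenly.

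**The case against.** The strongest reply is that nothing is lost. A move from none to severe is an event in outcomes 1 and 2, both of which are compared between arms, and the shift table gives its count by treatment. Anyone can add up the cells at 15 or more. This stands: a reader might infer that new-onset severe depression goes unanalysed, and the SAP does not support that. What the shift table does not do is name reaching 15 or more as an outcome to be compared. Applying the general Fisher's exact default in SAP 4.6 to that table would not create one either.

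A reader might also take 15 to be an automatic stopping threshold. It is not: Protocol 7.1 calls for referral to inform the decision and allows a participant to continue on randomized treatment. Nor is protection of individuals affected, since referral under 8.3.2.13 applies whatever the baseline score. Depression adverse events and the C-SSRS have their own analyses (SAP 4.6.5.9 and 4.6.5.9.2).

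The three outcomes can be read as deliberate overlapping steps, with the none group tested at the lower cut of 10. That is a coherent design, and no document promises a comparison of everyone reaching 15. Event counts would also be small, about 3 to 8 per arm on the assumptions above, and safety tests carry no multiplicity control (SAP 2.1), so a p-value would add little to the counts. These points limit the importance of the gap. They do not give a reason for leaving the non-depressed group out of the one outcome set at the protocol's own action score.

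Lastly, inadvertent enrolment (Protocol 7.2.2) could bring in a few participants with a baseline of 15 or more. They are outside outcome 3 as it stands and would remain outside it after the change.

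**Conclusion.** The gap is real but limited. The only named between-arm PHQ-9 comparison whose event is 15 or more counts four of the six category moves by which an eligible participant can get there. The two it omits are those starting from no depression. That conclusion rests on the SAP and protocol text alone.

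The share of events missed, about 13% to 57%, rests entirely on the assumed baseline share and risks and should be read as illustrative. The plan is neither contradictory nor impossible to carry out, and the omitted moves are visible elsewhere in the analysis. The point is a low-cost improvement to a safety comparison; it has no bearing on the efficacy conclusions or on the care of participants.

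**What to change.** In SAP 4.6.5.9.1, redefine the third outcome as an increase from None, Mild or Moderate to Moderately Severe or Severe (PHQ-9 of 15 or more). Its population would be all participants whose maximum baseline score is below 15 and who have a postbaseline score. Keep outcomes 1 and 2 unchanged. If comparability with the stepped definition now in the SAP is wanted, report the mild-or-moderate subset alongside.

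The cost is one line of SAP text, a small departure from the stepped definitions and, if the subset is kept, one extra display. No new data or visits are needed, and no alpha is spent, because safety assessments are outside the multiplicity scheme.
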